5.1. Sample size calculation

Using G*Power to perform a sample size calculation for a between-groups analysis of covariance (ANCOVA), with 80% power, an alpha level of 0.05, and controlling for intake severity to detect an effect size of d=0.6 (based on the CPM 1 trial (ISRCTN34503872) - converts to f=0.30) estimates that at least 45 participants are needed in each group (total sample size of 90).

Accounting for a drop-out rate of 50% (based on the lost-to-follow-up rate at 6-month follow-up in CPM 1), would inflate the total required sample size to a minimum of 180 (90 in each group). This high dropout rate is associated with the busy nature of healthcare, which makes it difficult to retain NHS staff in clinical trials, and hence it is essential to work to a conservative sample size calculation.

For reference, CPM 1 recruited a total of 173 participants (G1=83, G2=90). So, if we were to account for the expected follow-up drop-out rate, we would need to recruit more participants than CPM 1. Therefore, to ensure that the trial is adequately powered and robust to the expected level of attrition, we propose to recruit a minimum of 180 participants and to continue to recruit as many participants as are willing to provide consent within the 3-month recruitment period. In order to ensure the trial recruits to target and is robust to attrition, we will recruit from multiple NHS service providers across England.

5.2. Primary analysis

Trial data will be summarised using a CONSORT diagram and all analyses will be based on *intention-to-treat* principles (e.g., including all available data for participants who never attended intervention sessions, those who attended all sessions, and those who dropped out after a few sessions). Intention-to-treat principles will be followed to minimise well-known biases present in "completer analysis" (e.g., only including data from those who complete the intervention, who may not be representative of the wider population of eligible participants in need for treatment) and to follow best practice principles in healthcare research (White et al., 2011). Missing data will be imputed using an expectation-maximization algorithm, prior to conducting formal analyses.

The primary hypothesis test will be based on comparing mean OLBI (total severity) scores between groups at week 10 (post-intervention), as shown in Figure 1. Mean OLBI scores (dependent variable) will be compared between groups using ANCOVA, adjusting for baseline severity and entering "intervention group" as an independent variable. Adjusted 95% confidence intervals will be calculated around the adjusted mean difference between interventions. The analysis will be conducted using the Statistical Package for the Social Sciences (SPSS) by a researcher who will be blind to the label of the interventions. The primary analysis will be conducted using imputed data, following intention-to-treat principles. Secondary analyses will repeat the above ANCOVA model using per protocol analysis (only including participants that actually started the intervention; and excluding data from those in the 'non-intervention' group) and an unimputed dataset (e.g., completers analysis), to test the robustness and stability of the main analysis.

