Randomization and data collection	Consenting NHS doctors will be randomly assigned to two groups; 1 and 2. Participants in both groups will be asked to complete outcome measures at an initial baseline assessment, after which only participants in group 1 will access an 8-session, 10-week intervention (controlled phase). Next, group 2 will access the intervention during an 8-session, 10-week period (full implementation phase). Finally, we will collect further outcome measures 6 months after both groups have completed the intervention (follow-up phase). Following intention-to-treat principles, participants who do not attend any intervention sessions (and who do not formally withdraw) will be included in the study and will be invited to complete measures.	
Planned Sample Size	Minimum recruitment target of 180 participants, expecting 50% attrition, plus approx. 120 non-intervention participants.	
Data analysis method	 Trial data will be summarised using a CONSORT diagram and analyses will be based on intention-to-treat principles. The primary analysis will compare between-group differences in OLBI at 10-weeks, using ANCOVA adjusting for baseline OLBI. Secondary analyses: Between-group comparisons will be conducted at each measurement point using ANCOVA adjusting for baseline severity in the relevant outcome measure. Between-group and within-group effect sizes will be calculated using Cohen's d. Completion / dropout rates will be compared between groups using chisquare analysis. Predictors of dropout and treatment response will be examined as a secondary analysis using Elastic Net regularization Variability in burnout, wellbeing and job satisfaction will be examined across groups defined by job role and demographic characteristics using t-tests and appropriate non-parametric tests. Qualitative data will be analysed using thematic analysis. 	
Study Period	24 months (18 months active study period, plus 6 months analyses and dissemination)	

2. Background and rationale

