- After Group 1 has completed the ten-week, eight session intervention, the second group will have access to the same intervention using the process outlined above in Figure 1.

Data collection and safeguarding procedures

All participants irrespective of group allocation will be asked to complete the primary and secondary
measures described above, at four assessment points, as described in the 'Measures' section above.
 The measures will be collected by an independent NHS-based research team, who is not involved

directly in the intervention delivery. The researchers will use a secure, web-based, data collection system called Qualtrics.

- The consent and demographic questionnaires will ask for the participant's preferred email address. This is to ensure we are able to contact the participants throughout the study period (e.g., sending email reminders). Once they have completed the consent form we will email the participants a unique participant pseudonym, which cannot personally identify any of the study participants. The participant will then use this pseudonym to identify themselves throughout the rest of the study (i.e., to log in to the Microsoft Teams webinar). The research team will keep a record of the participant's email address and associated pseudonym, so if the participant forgets their code they can contact the team to retrieve these details. Staff in the research team will schedule the MS Teams sessions and will invite participants using their email addresses (this is required for the breakout session facility to be used). All participants' email addresses will be deleted after 2 years, which is a time-scale that we expect will allow sufficient time for the study to be concluded and to enable the research team to communicate all of the relevant results to participants via email.
- The measures will be collected by the research team using a secure, web-based, industry-standard data collection system. Therefore, all data collection will be in electronic form. Participants will receive email reminders (sent confidentially by the research team) at the relevant measurement points (see Figure 1). A maximum of 3 reminder emails will be sent to non-responding participants at each of the measurement points. If participants do not respond after the 3 reminders, we will consider that specific data-point to be missing. To access the survey, each participant will click on the link to access the survey via Qualtrics.

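### The primary ANCOVA is run on outcomes filled in by EM with no pooling or variance correction, so its standard error or its estimate is wrong, depending on an unstated EM model

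*Protocol*

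**What the plan says.** Protocol section 5.2 fixes both the method and the order of steps. First, "Missing data will be imputed using an expectation-maximization algorithm, prior to conducting formal analyses". Then the week-10 OLBI total is compared between groups by ANCOVA adjusted for baseline, with a 95% confidence interval around the adjusted difference, and "The primary analysis will be conducted using imputed data, following intention-to-treat principles". An unimputed version and a per-protocol version are named only as secondary robustness checks. Section 5.3 repeats the analysis at week 44, and at weeks 10 and 44 for the OLBI subscales, well-being and job satisfaction.

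Section 4.4 defines a missing outcome: "If participants do not respond after the 3 reminders, we will consider that specific data-point to be missing".

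Section 5.1 sizes the trial "with 80% power, an alpha level of 0.05, and controlling for intake severity to detect an effect size of d=0.6" and "estimates that at least 45 participants are needed in each group (total sample size of 90"). It continues: "Accounting for a drop-out rate of 50% (based on the lost-to-follow-up rate at 6-month follow-up in CPM 1"), which "would inflate the total required sample size to a minimum of 180 (90 in each group"). No expected loss at week 10 is given anywhere.

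**The concern.** A score filled in from a fitted model is not an observation. An ordinary ANCOVA on the completed data cannot tell the two apart: it counts every filled-in participant in the degrees of freedom and gives each one full weight in the variance. The sample-size section treats lost participants as lost information (180 recruited to keep 90), whereas the analysis section tests as though all 180 had responded. What is at stake is the primary p-value and confidence interval, and the between-group comparisons in section 5.3 that repeat the same model.

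**Working it through.** **Inputs from the protocol (section 5.1).** Alpha 0.05, power 80%, d = 0.6 (f = 0.30), one covariate, 90 evaluable, 50% loss, 180 recruited in two equal groups.

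**Assumptions, because the protocol is silent.** Fraction missing at week 10, m: 10% to 50%. Baseline–outcome correlation 0.6 (0.4 and 0.8 also tried). Outcomes missing completely at random. An EM model using baseline OLBI, with or without arm.

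**Step 1: reproduce the plan's figure.** Noncentral F with λ = f²N = 0.09 × 90 = 8.1 and 1 and 87 degrees of freedom gives power 80.4%. Then 90/(1 − 0.5) = 180. Both stated numbers reproduce. If all 180 were truly observed, power would be 97.9%; that gap is the information that imputation cannot create.

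**Step 2: arm included in the EM model.** Let σ be the residual SD.

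- *Conditional-mean fill-in.* The true SE is 2σ/√(N(1 − m)). Filled-in points lie on the fitted line and add nothing to the residual sum of squares, so the residual variance is about σ²(1 − m) and the reported SE is 2σ√(1 − m)/√N. The ratio of reported to true SE is 1 − m.
- *One random draw per missing score.* The true variance is (4σ²/N)[1/(1 − m) + m] and the reported variance is 4σ²/N. The ratio is 1/√(1/(1 − m) + m).

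The actual type I error is 2[1 − Φ(1.96 × ratio)]. At m = 0.5, mean fill-in gives 1.96 × 0.5 = 0.98, hence 32.7%. One draw gives 1.96 × 0.632 = 1.24, hence 21.5%.

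| Missing | SE ratio, mean | SE ratio, draw | Type I error, mean | Type I error, draw |
|---|---|---|---|---|
| 10% | 0.90 | 0.909 | 7.8% | 7.5% |
| 20% | 0.80 | 0.830 | 11.7% | 10.4% |
| 30% | 0.70 | 0.761 | 17.0% | 13.6% |
| 40% | 0.60 | 0.696 | 24.0% | 17.3% |
| 50% | 0.50 | 0.632 | 32.7% | 21.5% |

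The ratio does not depend on N, so recruiting beyond 180 does not help.

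Simulation (N = 180, 4,000 runs per scenario) agrees. Type I error (mean, draw) was 12.0% and 10.3% at 20% missing, 16.7% and 14.5% at 30%, and 32.1% and 20.9% at 50%. At 50% under mean fill-in, the average reported SE was 0.084 against a true 0.167. With a true effect of d = 0.6, 95% interval coverage was 88.5% and 89.6% at 20% missing, and 66.7% and 78.6% at 50%. At 50% missing under mean fill-in, correlations of 0.4 and 0.8 gave type I errors of 33.8% and 32.9%, so the assumed correlation hardly matters.

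**Step 3: arm omitted from the EM model.** Filled-in scores then carry no difference between arms, so the estimate is (1 − m) times the true effect. The simulated true effect was 0.48, which is 0.6 × the residual SD of √(1 − 0.36) = 0.8.

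| Missing | Expected (1 − m) × 0.48 | Simulated, mean fill-in | Coverage, mean | Coverage, draw |
|---|---|---|---|---|
| 20% | 0.384 | 0.383 | 85.6% | 87.7% |
| 30% | 0.336 | 0.335 | 69.8% | 77.2% |
| 50% | 0.240 | 0.237 | 20.5% | 49.9% |

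Under no effect, type I error stayed between 4.5% and 5.5%.

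**Step 4: the alternatives.** Multiple imputation (20 imputations, Rubin's rules, 1,500 runs) gave type I error 4.8%, coverage 94.5% and power 94% at 20% missing. At 50% missing it gave 5.5%, 95.5% and 77%. The ANCOVA on observed scores at 50% missing gave 5.1%, 95.0% and 79%.

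**Step 5: which loss rate applies.** The 50% comes from the 6-month follow-up of CPM 1. In this trial, follow-up at week 44 is 44 − 20 = 24 weeks after the second group finishes. So 50% is close to the protocol's own expectation for the repeated week-44 analysis, and an upper-end value for week 10.

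**The case against.** Several points on the other side are fair.

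- *A reader might infer that the p-value is always too optimistic.* The protocol does not support that, because it does not say whether arm is in the EM model. If arm is omitted, the test keeps its size and the effect is understated. The interval still fails when there is a true effect.
- *A reader might take 33% as the type I error of the primary test.* That needs half the week-10 scores to be missing, arm in the model and conditional-mean fill-in. The protocol gives no week-10 rate, still invites non-attenders to complete questionnaires, and sends up to three reminders. At 20% missing the figure is 10 to 12%: smaller, but still about double nominal.
- *Filled-in scores need not be empty of information.* Outcome scores are also collected at weeks 20 and 44, and the other scales at week 10. An EM model using them borrows real information, which would reduce the understatement of the SE but not remove it.
- *A reader might infer that non-responding never-attenders are filled in from attenders, so that the intention-to-treat effect is overstated.* This could happen, but its size needs response rates by attendance, which the protocol does not give. It is not caused by single imputation either: an unimputed ANCOVA, or multiple imputation that ignores attendance, would share it.
- *Single imputation is inferred, and a SAP may exist.* Details such as the number of imputations or a missing-not-at-random analysis can be left to a SAP, and their absence is not criticised here. But section 5.2 does name the method, the order of steps and the dataset for the primary test, and one completed dataset is the natural reading.
- *The unimputed ANCOVA is prespecified.* Its standard error is valid if scores are missing at random given baseline and arm. It will sit beside the primary result, but as a secondary check it does not protect the primary p-value or interval.

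**Conclusion.** Wrong as written. Followed literally, section 5.2 produces either a standard error that is too small or an effect that is too small, and the protocol does not determine which.

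With arm in the EM model, nominal 5% becomes about 8% at 10% missing, 10 to 12% at 20%, 14 to 17% at 30% and 22 to 33% at 50%. The lower figures are for one stochastic draw and the higher for conditional means. With arm omitted, type I error stays near 5%, but the effect is multiplied by the observed fraction and coverage falls below 95%.

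The figures assume outcomes missing completely at random and an EM model with baseline OLBI as its only covariate besides arm. They hardly move with the baseline correlation. The upper end is a bound for week 10 and a realistic value for the week-44 repeat.

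**What to change.** In section 5.2, replace the EM sentence with one of two options:

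- Multiple imputation with arm, baseline OLBI, site and the other collected outcome scores in the imputation model, and the ANCOVA results combined by Rubin's rules. Session attendance should enter the week-10 model for Group 1 only: Group 2 starts its sessions after week 10, so there attendance is either zero or a post-outcome variable. If week-20 and week-44 scores are used, imputing separately by arm is a simple way to include arm, because Group 2 receives the intervention between weeks 10 and 20.
- A likelihood-based model fitted to the observed scores.

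Apply the same choice to the secondary ANCOVAs in section 5.3.

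The change needs wording and a little more analysis work, with no new data or recruitment. If arm was to be in the EM model, the reported interval will be wider and will cover as stated. Even at 50% missing, simulated power at d = 0.6 was 77% with multiple imputation, close to the planned 80%.

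### The primary ANCOVA is run on EM-imputed scores with no step that carries imputation uncertainty into its confidence interval or p-value, so the primary interval is invalid whether or not trial arm is in the EM model

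*Protocol*

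**What the plan says.** Section 5.2 of the protocol fixes the handling of missing scores in two sentences: "Missing data will be imputed using an expectation-maximization algorithm, prior to conducting formal analyses" and "The primary analysis will be conducted using imputed data, following intention-to-treat principles". The primary model is an ANCOVA of week-10 OLBI total on randomised group and baseline OLBI, reported with a 95% CI for the adjusted mean difference. The section mentions neither several imputed datasets nor a pooling rule, bootstrap or variance correction. It does not say which variables enter the EM model, or whether trial arm is one of them. An ANCOVA on the unimputed data is listed as a secondary robustness check.

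Section 5.3 repeats the ANCOVA at week 44. It also applies it to the OLBI sub-scores, WEMWBS and job satisfaction at weeks 10 and 44, and adds paired within-group comparisons with baseline.

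Section 5.1 sizes the trial "with 80% power, an alpha level of 0.05, and controlling for intake severity to detect an effect size of d=0.6", which gives 90 evaluable participants. It then doubles this to 180: "Accounting for a drop-out rate of 50% (based on the lost-to-follow-up rate at 6-month follow-up in CPM 1"). No separate missing rate is given for week 10.

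**The concern.** A score filled in by EM is a prediction from the other participants' data. It adds no information and, in a deterministic fill, has no residual scatter. An ordinary ANCOVA on the completed file counts it as an independent observation. The residual variance falls while the sample size and degrees of freedom stay at their full values, so the standard error comes out too small.

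The trial's one confirmatory test and its confidence interval rest on this calculation, and heavy loss is expected. The same data handling extends to the secondary ANCOVAs and, as the text reads, to the paired comparisons.

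This point concerns the error bars and, if arm is omitted from the EM model, the attenuation that follows. It does not concern bias from informative loss.

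**Working it through.** **Inputs from the protocol (section 5.1).** Alpha 0.05, power 80%, d = 0.6 (f = 0.30), 90 evaluable, 180 recruited (90 per group), 50% loss at 6 months in the earlier trial.

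**Assumptions not in the protocol.** Baseline to week-10 correlation r = 0.6 (0.3 and 0.8 also tried). Outcomes missing completely at random, at the same rate in both arms. Outcome scaled to SD 1.

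**Step 1: the plan's own figure.** ANCOVA F test with 1 numerator df, two groups and one covariate, noncentrality f²N. At N = 90: 0.30² × 90 = 8.1 on 1 and 87 df, power 80.4%. N = 89 gives 79.9%. So 90 is the smallest adequate N, and 90 / (1 - 0.5) = 180. The sample size reproduces.

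**Step 2: arm in a deterministic EM fill.** Let s² be the residual variance given baseline and m the share missing.
- Reported: the filled scores lie on the fitted line, so residual variance is about (1-m)s² over N records. SE = sqrt[(1-m)s² × 4/N].
- True: only N(1-m) scores carry information. SE = sqrt[s² × 4/(N(1-m))].
- Ratio: reported / true = 1-m.
- Rejection rate under no effect: 2 × [1 - Φ(1.96(1-m))].

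At N = 180, m = 0.5, r = 0.6: s² = 1 - 0.36 = 0.64. Reported SE = sqrt(0.5 × 0.64 × 4/180) = 0.084. True SE = sqrt(0.64 × 4/90) = 0.169. Ratio 0.50, and 1.96 × 0.50 = 0.98, which gives 32.7%.

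| Missing m | Ratio, formula | False positives, formula | Ratio, simulated | False positives, simulated |
|---|---|---|---|---|
| 10% | 0.90 | 7.8% | 0.90 | 7.6% |
| 20% | 0.80 | 11.7% | 0.80 | 11.7% |
| 30% | 0.70 | 17.0% | 0.68 | 18.0% |
| 40% | 0.60 | 24.0% | 0.59 | 24.1% |
| 50% | 0.50 | 32.7% | 0.48 | 33.7% |

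The simulations used 4,000 runs per row. A second simulation gave 12%, 16% and 33% at 20%, 30% and 50% missing. The 50% result does not depend on r (33.8% at r = 0.3, 33.7% at r = 0.8).

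**Step 3: comparator.** ANCOVA on the observed outcomes only, at 50% missing: mean reported SE 0.170 against a true 0.168, false-positive rate 4.8%.

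**Step 4: milder versions of a single fill, at 50% missing.**
- Random residual added to each filled score: reported variance is proportional to 1 and true variance to 1/(1-m) + m = 2 + 0.5 = 2.5. The ratio is 1/sqrt(2.5) = 0.63, and 1.96 × 0.63 = 1.24 gives about 21.5%. Simulations gave 21-22%.
- A fully observed auxiliary variable in the EM model, with partial correlation 0.3, 0.5 or 0.7: 29.7%, 24.7% and 17.5%.

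**Step 5: arm left out of the EM model.** Filled scores then carry no group difference, so the estimate is about (1-m) times the true effect. At 50% missing, 0.60 × 0.5 = 0.30 (simulated 0.30, reported SE 0.087). The false-positive rate is 5.0%. Coverage of the true 0.60 is about Φ(1.96 - 0.30/0.087) = Φ(-1.49) = 7%; direct simulation gave 8%.

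**The case against.** Four objections deserve an answer.

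- **The week-10 missing rate is unknown.** This stands. The 50% is a 6-month figure that section 5.1 uses as a cautious planning value. Non-attenders are still sent the questionnaires (section 4), so missing sessions does not mean missing outcomes. A reader might infer that the primary test will have a false-positive rate near one in three. The protocol does not support that, because 33% needs 50% missing at week 10. At 10-30% missing the rate is about 8-18%. The 50% applies most directly to the week-44 repeat of the analysis.

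- **The inflation depends on arm being in the EM model.** This also stands. The protocol does not say, and a statistical analysis plan not at hand may list the variables. An unconditional statement that the 5% level is breached is therefore not established. It does not rescue the method, because without arm the estimate is attenuated and the interval misses the truth.

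- **A single completed file is inferred.** True, but it is the natural reading of filling by EM before the analyses with no pooling rule. Adding a random residual softens the result without curing it.

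- **The unimputed ANCOVA is prespecified, so a discrepancy would be seen.** Partly right. But it is secondary, no rule covers disagreement, and the headline interval remains the one from imputed data.

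A reader might also see a contradiction between powering on 90 in section 5.1 and analysing 180 in section 5.2. There is none: inflating for attrition and then analysing everyone randomised is ordinary practice. The fault is only in how the filled records are counted in the standard error.

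**Conclusion.** The concern holds in this form: section 5.2 commits the primary analysis to imputed data without carrying imputation uncertainty into the CI or p-value, and the resulting interval is invalid on either reading of the EM model. This is a stated method, not a detail left for later.

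- **Arm in a deterministic fill:** false-positive rate about 12% at 20% missing, 16-18% at 30% and 33% at 50% (about 22% at 50% if a residual is drawn once).
- **Arm left out:** type I error near 5%, with the effect reduced by about the missing share and CI coverage of about 8% at 50% missing.

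The figures assume missingness at random (simulated as completely at random, with equal rates by arm) and ordinary ANCOVA on one completed file. The actual size at week 10 depends on a missing rate that the protocol does not give. Because the fault lies in the sole primary test and is cheap to correct, it should be fixed before the analysis.

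**What to change.** Replace the EM sentence in section 5.2 with one of these as the primary analysis:

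- multiple imputation done separately by randomised group, with the ANCOVA fitted in each dataset and estimates and standard errors combined by Rubin's rules; or
- a likelihood-based mixed model on all observed waves, with the week-10 group difference as the primary contrast.

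Use the same approach for the secondary ANCOVAs in section 5.3, including week 44, and for any paired comparison that uses imputed data. State that no single EM-filled dataset is used for inference.

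**Cost:** a change of wording, slightly more analysis work, and a wider CI. Planned power is kept as long as no more than half the week-10 outcomes are missing, because section 5.1 already counts only 90 informative participants (80.4% at f = 0.30). Recruitment need not change.

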3.3. Hypotheses

[figure not shown]
- A) Exposure to the intervention will be associated with significantly lower mean burnout severity by comparison to a waitlist (delayed intervention) control group
- B) After the control group is exposed to the intervention, there will be no significant differences in mean burnout level between the two groups (immediate intervention group, delayed intervention group)
- C) Mean burnout severity for all participants at the end of the 6-month follow-up period will be significantly lower than baseline severity (prior to intervention), but not significantly different to endof-treatment severity, indicating maintenance of gains

4. Study design

This will be a pragmatic, stepped wedge, open-label, randomised controlled trial. Consenting doctors will be randomly assigned to two groups, by a research assistant using a computerized randomization algorithm. The randomisation sequence will be based on random blocks of 10 participants, and

stratification according to participants' employing organisation (trial site). The study will be carried out in three phases, which are illustrated in Figure 1.

Figure 1. Stepped wedge trial design

Participants in both groups will be asked to complete outcome measures during a pre-intervention baseline assessment (week 0). After the baseline assessment, only participants in group 1 will access an 8 session, 10-week intervention (controlled phase). Next, group 2 will access the intervention during a 10-week period (full implementation phase). Finally, we will collect further outcome measures 6 months after both groups have completed the intervention (follow-up phase). Selected outcome measures (see section '4.3 Measures' for more details) will be completed at each of the measurement points outlined in the above timeline (weeks 0, 10, 20, 44). All measures will be completed online using an industry-standard survey system (Qualtrics), which will be managed by a research assistant.

The end of the study is classed as once the participant has completed the six-month follow-up questionnaire. However, the participants email addresses will be kept for up to six months after this to ensure the research team can disseminate the results of the study. Following this, all personal data will be deleted.

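### Randomisation is stratified by employing organisation, but the ANCOVAs omit it, so if site is prognostic the reported standard errors will not reflect the stratified design

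*Protocol*

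**What the plan says.** Section 4 (Study design) of the protocol fixes the allocation method: "The randomisation sequence will be based on random blocks of 10 participants", with "stratification according to participants' employing organisation (trial site"). Section 5.1 adds that recruitment will be from several NHS providers across England, without giving a number.

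Section 5.2 sets the primary model: "Mean OLBI scores (dependent variable) will be compared between groups using ANCOVA, adjusting for baseline severity and entering" the intervention group as the independent variable. The synopsis agrees, describing the week-10 comparison as made "using ANCOVA adjusting for baseline OLBI". The per-protocol and unimputed analyses in section 5.2 reuse that model. Section 5.3 repeats it at week 44 and for the OLBI sub-scales, well-being and job satisfaction, controlling only for the matching baseline score. No model contains site, and no reason is given for leaving it out.

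**The concern.** Stratified blocks hold the arms nearly equal in size within each site. Differences between sites then largely cancel out of the arm comparison and add little to its true variance. A model without site does not know this and keeps the between-site variation in its residual. If site is related to the outcome after baseline adjustment, the reported standard error overstates the real uncertainty: intervals are too wide and the test rejects less often than its nominal level.

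Such a relation is plausible. Section 4.1 spans community general practice to specialist hospital services. Section 2 cites burnout risk of 32% in GPs, 18% in specialists, 11% in doctors in training and 7% in SAS and LE doctors, and employing organisation will partly separate these groups. Baseline OLBI will absorb some of that difference. How much remains is unknown.

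What is at stake is whether intervals and p-values have their stated properties, plus a little power in a trial that expects heavy attrition.

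**Working it through.** **1. The plan's own figure.** Section 5.1 plans "with 80% power, an alpha level of 0.05, and controlling for intake severity to detect an effect size of d=0.6", which "converts to f=0.30". For an ANCOVA with two groups and one covariate, the noncentrality is f² × N = 0.09 × 90 = 8.1 on 1 and 90 − 3 = 87 degrees of freedom. Power is 80.4%, and 90 is the smallest N that reaches 80%. Allowing for 50% loss, 90 / 0.5 = 180. Both figures reproduce, and the site question does not change them.

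**2. Closed-form size of the effect.** Let ρ be the share of residual (baseline-adjusted) OLBI variance due to site, with k equal sites and arms fully balanced within each. Relative to a total residual variance of 1:
- true variance of the arm difference ∝ 1 − ρ
- variance reported without site ∝ (1 − ρ) + ρ(k − 1)/k = 1 − ρ/k
- reported SE / true SD = √[(1 − ρ/k) / (1 − ρ)]

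The protocol gives neither ρ nor k, so both are assumed.

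| ρ | k = 4 | k = 8 | k = 15 |
|---|---|---|---|
| 0.02 | 1.008 | 1.009 | 1.009 |
| 0.05 | 1.020 | 1.023 | 1.024 |
| 0.10 | 1.041 | 1.047 | 1.051 |
| 0.15 | 1.064 | 1.074 | 1.079 |

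Incomplete blocks and unequal sites make the realised effect somewhat smaller.

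**3. Simulation, all 180 analysed.** Assumptions: 12 sites, blocks of 10 within site, baseline correlation 0.6, 3,000 null trials per setting.

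| ρ | Reported SE, no site | Empirical SD, no site | Reported SE, with site | Type I error, no site |
|---|---|---|---|---|
| 0.05 | 0.1194 | 0.1162 | 0.1169 | 4.4% |
| 0.10 | 0.1191 | 0.1138 | 0.1137 | 4.1% |
| 0.15 | 0.1188 | 0.1127 | 0.1104 | 3.7% |

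Reported SE over empirical SD is 1.028, 1.047 and 1.054. An SD estimated from 3,000 runs has a relative error of about 1/√6000 = 1.3%, so these agree with the closed form. A second simulation with unequal sites (4, 8 and 15) at 180 gave 1.01-1.02 at ρ = 0.05, 1.04-1.05 at 0.10 and 1.08-1.09 at 0.20.

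**4. Does adding site sharpen the estimate, or only the reported SE?** Compare the empirical SD of the planned estimator with the with-site SE:
- ρ = 0.05: (0.1162/0.1169)² = 0.99
- ρ = 0.10: (0.1138/0.1137)² = 1.00
- ρ = 0.15: (0.1127/0.1104)² = 1.04

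The true gain in precision is about −1%, 0% and 4%. The second simulation agrees: with 8 sites and 180 analysed, the empirical SDs without and with site were 0.141 and 0.141 at ρ = 0.10, and 0.135 and 0.134 at 0.20. Stratified allocation has already delivered most of the precision. The planned model does not report it.

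**5. Power at the planned 90 evaluable (d = 0.6, fixed site effects, no pooling).**

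| Sites | ρ | Without site | With site |
|---|---|---|---|
| 8 | 0.10 | 0.817 | 0.832 |
| 8 | 0.20 | 0.827 | 0.871 |
| 15 | 0 | 0.810 | 0.770 |
| 15 | 0.02 | 0.803 | 0.769 |
| 15 | 0.05 | 0.803 | 0.785 |
| 15 | 0.10 | 0.800 | 0.801 |
| 15 | 0.20 | 0.817 | 0.851 |

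With all 180 analysed, power is 97-99% under either model.

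**The case against.** **The effect is conditional and may be negligible.** This stands. Baseline OLBI absorbs stable site differences, and the intervention is delivered online in groups chosen by day and time, not by site. Nothing in the protocol shows a large residual site effect.

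**A reader might infer that omitting site throws away free precision.** Squaring the ratio of the two reported SEs in step 3 gives 1.04, 1.10 and 1.16, which could be read as the worth of 4%, 10% or 16% more participants. That is not supported. It compares what the two models report, not how variable the two estimators are, and step 4 shows a true gain near zero. Nor is it free: step 5 shows that with about 90 evaluable, many small sites and little site effect, fixed site terms cost power.

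**A reader might also infer that the primary analysis as a whole is conservative.** That is not established. Section 5.2 imputes missing data by an expectation-maximisation algorithm. If this yields a single completed dataset, the SE is understated. Unmodelled clustering in delivery groups of up to 30 (section 4.2) can also understate it. The net direction could go either way. These are separate issues, and neither is a reason to leave the stratification factor out.

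**Covariate lists are often left to a statistical analysis plan.** This has little force here. The protocol names its covariates in the synopsis and in sections 5.2 and 5.3, so the model is fixed without site.

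**Conclusion.** The mismatch between the stratified design and the analysis is real and stands in the protocol's text. Its consequence depends on site predicting the outcome after baseline adjustment. On assumed residual ICCs, with all 180 analysed, intervals are about 1-2% too wide at 0.05, 4-5% at 0.10 and 6-8% at 0.15, with type I error slightly below 5%. At 0.02 or less the effect is negligible. The main loss is that the reported error bars do not reflect the stratified allocation. The power lost is at most a few points, for example 0.827 against 0.871 at 90 evaluable, 8 sites and an ICC of 0.20.

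The treatment estimate is not biased, type I error is not inflated by this omission, and the figures of 90 and 180 stand. This is a modest point of coherence that is cheap to correct. The ICCs and numbers of sites are assumptions; the protocol gives neither.

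**What to change.** In sections 5.2 and 5.3, and in the synopsis, state that each ANCOVA adjusts for the baseline value of the outcome and for trial site, the stratification factor. Specify in advance how small sites are handled: either pool sites below a stated size (for instance fewer than 10 participants) into one category, or fit site as a random effect. Include site in the imputation model. If the sponsor prefers to omit site, the protocol should give the reason.

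The cost is one sentence and a few degrees of freedom. No new data are needed, because the stratum is known for every participant at randomisation. The downside is a loss of about 1-3 power points when there are many small sites, about 90 evaluable participants and little site effect (4 points in the worst setting run: 15 unpooled sites and no site effect). Pooling or a random effect limits that loss.
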